**Clinicaltrials.gov Title:
Response Inhibition in Tourette Syndrome**

NCT03628703

**Latest version approved by IRB: 4/2/2020
Title below is the local IRB protocol title**

**I. TITLE: Preliminary Investigations of Transcranial Magnetic
Stimulation (TMS) to understand Diseases and Disorders that affect the
Motor System in Children**

I. ABSTRACT

Automatic and purposeful movements require signaling from the brain and spinal cord (central nervous system - CNS) via the nerves (peripheral nervous system - PNS) to muscles. Abnormal input into this pathway from the basal ganglia or cerebellum results in disorders of movement regulation and coordination. Diseases of the brain and spinal cord (central nervous system) can lead to weakness. Motor pathways can be assessed through testing of clinical properties of movement, such as strength, bulk, tone, reflexes, movement regulation, and coordination. Motor pathways can also be quantified through measurement of three fundamental neurophysiological properties: 1) the threshold (the amount of energy required to generate nerve firing); 2) the latency (the amount of time it takes for an electrical signal to propagate between two points of interest in the nervous system); and 3) the amplitude (the size of the response, which reflects the number of nerve cells that have activated). This testing is analogous to Peripheral motor system assessment performed routinely using Electromyography / Nerve Conduction Studies (EMG/NCS). Recent research has shown that Transcranial Magnetic Stimulation (TMS) may be used for this purpose but, unlike EMG/NCS, TMS is not yet FDA Approved for routine motor system diagnostics in the United States (although repetitive TMS is cleared by the FDA for treatment of depression). At Cincinnati Children's Hospital Medical Center (CCHMC), our laboratory has been using TMS for research in children and adults to understand normal motor system development, and abnormal motor function in Attention Deficit Hyperactivity Disorder (ADHD) and Tourette Syndrome (TS) for over 5 years. In this study we propose a preliminary investigation to assess feasibility of use of TMS for diagnostic purposes. Our primary aims are: 1) to use TMS to collect neurophysiologic data in children with motor disorders, 2) to use TMS to generate hypotheses and preliminary findings in motor system diseases which can be used for preliminary data in future scientific studies and grant applications.

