CCHMC has a large and diverse group of specialists that treat diseases and disorders of the central nervous system. Clinicians include neurologists, neurosurgeons, orthopedic surgeons, physiatrists, radiologists, psychiatrists, and psychologists. A vast array of imaging technologies provides exquisitely sensitive and anatomically specific information about neurological diseases. Imaging techniques in use at CCHMC include Computed Tomography (CT), Magnetic Resonance Imaging (MRI) (1.5 and 3 Tesla magnets), Functional MRI, Single Photon Emission Computed Tomography (SPECT), and Positron Emission Tomography (PET). Because the nervous system uses electro-chemical signaling, the central nervous system may also be assessed with neurophysiological techniques including electroencephalography (EEG) and magnetoencephalography (MEG). Each of these studies provides useful information, but has some limits in terms of sensitivity, specificity, time, cost, need for sedation, and patient tolerability. TMS may ultimately join these other technologies in providing useful clinical information to a wide variety of specialties.

This possibility can be understood through describing some representative scenarios:

Clinical scenarios

Acute Spinal cord disease - transverse myelitis: child presents with progressive and ultimately complete flaccid paralysis of the legs. MRI imaging shows signal change for 2

cm in the thoracic spinal cord, consistent with a diagnosis of *transverse myelitis*. Clinical question: is there preservation of motor pathways to the legs?

TMS tests: Double cone coil over vertex, round coil over lumbar spine/plexus. Surface EMG over lower leg (anterior tibial) muscle.

Possible results: Lumbar plexus stimulation produces normal responses in the legs. Brain stimulation shows prolonged latency (slow conduction time) from brain to lower spine, with small amplitude motor evoked potential in the leg. This suggests that despite complete loss of movement of the legs and signal change in spinal cord, there are some preserved, intact motor fibers running through the spinal cord. Injury involves both demyelination and axonal damage. (Note - Somatosensory Evoked Potentials are currently used clinically to assess sensory pathways in spinal cord. TMS could complement this by assessing motor pathways. TMS is also much quicker and probably more comfortable.)

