Cerebellum - ataxia: A new therapy is developed for a degenerative ataxia, e.g. for Friedreich's ²³. Investigators wish to monitor the effects with a simple, short clinical test that does not require sedation. Ataxia is challenging to accurately rate. Question: Is cerebellar-cerebral inhibition a biomarker of cerebellar response to treatment?

TMS tests: Paired pulse cerebellar/motor cortex.

Possible results: Drug treatment, but not placebo treatment, is associated with a normalization of neurophysiological measures.

Metabolic or genetic leukodystrophies: A new therapy is developed for a degenerative white matter disease. Clinical rating scales of disability and impairment are insensitive to early effects of treatment. Clinical question: Is central conduction a biomarker of white matter regeneration and repair?

TMS tests: Single pulse TMS in motor cortex; paired pulse cerebellar/motor cortex.

Possible results: Beneficial treatment modifies central conduction velocities, predicting clinical subsequent improvement.

Possible Psychogenic Disorder: Patient presents with abnormal movement(s) or paralysis. There is suspicion that the symptoms are psychogenic in origin. Clinical question: Are symptoms psychogenic? I.e. is motor system physiologically intact?

TMS tests: Double cone coil over motor cortex. Electrodes are place over limb.

Possible results: In psychogenic conditions, neurophysiologic results should be normal. This may save time and resources as it may eliminate the need for other costly or risky diagnostic tests.

IV. PREVIOUS WORK DONE IN THIS AREA

Transcranial Magnetic Stimulation (TMS) has been used in humans, in essentially its current form, for 20 years ²². Several companies make TMS devices. Each involves a pulse generator which stores electrical energy (from a wall outlet) connected to a hand-sized coil, usually round or figure-of-eight shaped. The operator or a computer can trigger the generator to release electricity into the coil which produces a transient magnetic field beneath the coil. When the field change occurs near neurons, they may depolarize (fire), producing a measurable response. The maximum field strength for the Magstim TMS device which we have used at CCHMC is 2 Tesla (comparable to 1.5 and 3 Tesla magnets used for clinical MRI scans).

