Neurophysiological parameters Thresholds defined using conventional criteria as the lowest stimulator intensity that produces measurable responses in 3 of 6 trials. Short intracortical inhibition (SICI) and facilitation (ICF) are measured with a paired-pulse paradigm using three conditions: single pulse, paired pulse at 3 msec interstimulus intervals, paired pulse at 10 msec interstimulus intervals. Subthreshold pulse precedes suprathreshold pulse for paired pulses. Peripheral conditioning pulses are administered 20-30 msec prior to motor cortex. Short ICF will be also performed with a paired-pulse paradigm ³⁸⁻⁴⁰. Long intracortical inhibition (LICI) involves using 100-200 msec interstimulus intervals. In other forms of paired-pulse stimulation such as cerebellar conditioning, pulses are administered 5-10 msec prior to motor cortex. Twenty trials are performed for each ISI and for the test stimulus alone. The order of the intervals is varied randomly, and the interval between trials varies randomly by <10% around a mean of 6 seconds. Transcortical inhibition to the left dominant hemisphere/ right dominant hand is measured by stimulating over right motor cortex, while the child simultaneously contracts muscles in both hands. This produces an evoked potential in this ipsilateral and contralateral hand, followed by periods of EMG silence (the “silent period”). Latency and duration of this silent period are affected both by age and by ADHD diagnosis ⁴¹. Latencies are measured by subtracting MEP onset time from TMS artifact time. Amplitudes are measured as peak to peak and area under the curve.

5. Questionnaires:

NA

6. Blood Specimens:

NA

7. Previous research studies in which the projected patient population may be involved:

There are no issues related to cumulative risk. Participation in several different TMS protocols is allowed but no individual would participate in 2 or more protocols the same day.

8. Data Analysis and Sample Size Calculations:

Sample size- general issues

We are requesting permission to enroll up to 300 children and adults. We wish to offer TMS as a potential clinically useful tool and for hypothesis generation in a variety of motor disorders. Statistical analyses otherwise are not planned.

a. The utility of TMS in motor disorders

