In adults, the sensitivity of TMS for spinal cord disease has been published as 100% and specificity 85% ¹⁶. Similarly, in adults loss of and preservation of motor potentials are highly predictive of poor vs. good long term outcomes after stroke ⁵.

b. Quantitative biological markers of motor system disease, assessed using TMS. We anticipate that TMS measurements listed in Table 1 will yield quantitatively abnormal responses, compared to the same measures in healthy children. However, this is a preliminary study, not a formal case-control study. Some of these data, such as complete absence of a response localizing to spinal cord or cerebrum, will be unambiguous. Other measures, similar to some neuroimaging results, may be interpretable in a clinical context. Finally, some measures may ultimately be useful for understanding disease, based on disease vs. control between group differences, in future studies.

c. Reliability and Consistency of TMS Data in our Lab.

Certain measures, such as central motor conduction times, have normative data published. We can use available data as a reference for the data we generate through use of TMS to determine whether data in our laboratory are broadly consistent with those published, but formal statistical analysis is not planned for this aim at this time. In addition, although we do not have funding at this time for generating normative and disease related pediatric datasets and test-retest datasets, we plan to store our data and thereby have some ability to assess this. We have previously published test-retest data in Tourette Syndrome and ADHD for a measure of motor cortex inhibition ⁴².

9. Facilities:

Studies will be performed in the Division of Neurology and Neurophysiology/TMS /MEG/EEG Laboratory at Cincinnati Children's Hospital Medical Center.

VII. SPECIAL CONSIDERATIONS

1. Radiation Safety: NA
2. Investigational Devices: The TMS apparatus is investigational, although it has recently been cleared for treatment of refractory depression. We consider 2 Tesla or less stimulation of brain, cerebellum, spinal cord, and nerves to be a non-significant risk use of the TMS device. Manufacturer's information for the

Magstim device has previously been submitted to the IRB and is available on request.

3. IND (Investigational New Drug): NA
4. Emergency Use: NA
5. CCHMC Pharmacy: NA.
6. Discarded Tissues: NA
7. Tissue Banks: NA
8. Genetic Studies: NA
9. Institutional Biohazard Committee: NA
10. Imaging: NA

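### The latency rule in VI.4 is worded in reverse, so taken literally it gives negative latencies and conflicts with the protocol's own definition of latency

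*Combined protocol and SAP*

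**What the plan says.** Section VI.4, under Neurophysiological parameters, gives the measurement rules for thresholds, latencies and amplitudes. For latency the rule is: "Latencies are measured by subtracting MEP onset time from TMS artifact time". It is the only latency formula in the document. No absolute value or sign convention is given there or elsewhere.

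Three other places show what latency is meant to be:

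- The Abstract names latency as one of three fundamental neurophysiological properties and defines it as "the amount of time it takes for an electrical signal to propagate between two points of interest in the nervous system".
- The transverse myelitis scenario in section III describes a possible abnormal result: "Brain stimulation shows prolonged latency (slow conduction time) from brain to lower spine".
- Section IV sets out the order of events: "When the field change occurs near neurons, they may depolarize (fire), producing a measurable response".

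On use of the data, section VI.8.c notes: "Certain measures, such as central motor conduction times, have normative data published". It proposes to use available data as a reference for broad consistency, without a formal test. The general paragraph of VI.8 adds: "Statistical analyses otherwise are not planned".

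**The concern.** The sentence is an operative measurement rule, set beside the rules for threshold and amplitude, and the order of its subtraction is the opposite of what an elapsed time requires. If someone computed latencies exactly as written and kept the sign, each value would be negative and the slowest pathway would have the lowest number. Any ranking from fast to slow would be inverted, and a direct comparison with positive published values would fail.

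The protocol intends to store its data, and section II expects other divisions to use the findings as preliminary data. A later user may therefore have only the written definition to go by.

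**Working it through.** This is a sign check. The plan states no latency figure, so there is none to reproduce.

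**Inputs from the protocol**

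- Rule as written (VI.4): latency = artifact time − MEP onset time.
- Meaning of latency (Abstract): elapsed time, hence positive.
- Order of events (section IV): the pulse comes first and the response follows, so onset time > artifact time.
- Direction of interpretation (section III): a larger latency means slower conduction.

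**General result.** Let the artifact occur at time *a* and the MEP begin at *a + L*, with *L* > 0.

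- As written: *a* − (*a + L*) = −*L*, which is negative for every *L*.
- With the terms swapped: (*a + L*) − *a* = +*L*.

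**Illustration.** The protocol gives no latency values. The artifact time of 100 ms and the true latencies below are assumptions. The sign result does not depend on them.

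| True latency (ms) | Onset time (ms) | As written (ms) | Terms swapped (ms) |
|---|---|---|---|
| 10 | 110 | 100 − 110 = −10 | 110 − 100 = +10 |
| 20 | 120 | 100 − 120 = −20 | 120 − 100 = +20 |
| 30 | 130 | 100 − 130 = −30 | 130 − 100 = +30 |
| 40 | 140 | 100 − 140 = −40 | 140 − 100 = +40 |

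As written, all four values are negative and they fall as conduction slows (−10 > −20 > −30 > −40). With the terms swapped, all are positive and rise as conduction slows, in agreement with the Abstract and section III.

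**What does not change.** The absolute values are the same in both columns. A contrast between two subjects keeps its size and loses only its sign: for true latencies of 30 and 20 ms, the written rule gives −30 − (−20) = −10 ms instead of 30 − 20 = +10 ms.

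**The case against.** The strongest reply is that nobody would be misled. The Abstract and section III make a positive elapsed time the only sensible reading, and a column of all-negative conduction times would be noticed at once. The reversal would apply equally to every subject, so group differences would keep their size and correlations their strength, and one multiplication by −1 would restore the sign. Thresholds and amplitudes are untouched, and no eligibility rule, sample size or formal test uses latency. All of this stands, and it limits the weight of the point. It does not make the sentence correct: the same passages that reveal the intent also contradict the rule.

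A reader might infer three stronger things that the documents do not support:

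- *That latencies have actually been computed with the wrong sign.* Nothing shows this. The protocol describes no analysis scripts and says only that signals are stored for analysis in named software.
- *That the protocol's central motor conduction time is reversed.* It would be, if that time were formed as a cortical latency minus a spinal or plexus latency. The protocol gives no formula for it, so this would be the reader's assumption.
- *That section VI.8.c relies on the comparison with published norms.* It describes an informal check of broad consistency and says that no formal statistical analysis is planned for that aim at this time.

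**Conclusion.** The point holds as a minor internal inconsistency. The only latency rule in the protocol, read literally, has the wrong sign for any response that follows its stimulus, and it conflicts with the Abstract and section III. This conclusion rests only on the ordinary meaning of subtracting one quantity from another and on the response coming after the pulse. It does not depend on the assumed millisecond values.

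It is very probably a drafting slip. The error is one of sign alone. It would matter only if the sentence were applied literally, the sign kept, and the values then ranked or set against published norms. It is worth correcting because the sentence defines a core measurement and the correction costs almost nothing.

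**What to change.** In VI.4, reverse the two terms: *Latencies are measured by subtracting TMS artifact time from MEP onset time.* Then confirm that latencies already stored were calculated in that direction. If any were not, reverse their sign.

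The cost is one sentence and a brief check of stored values. No change to design, sample size or analysis follows. This correction does not require adding a definition of central motor conduction time.

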The subject sits in a comfortable dental chair or lies prone on a hospital bed. The TMS devices are maintained in the EEG suite, which is under direct supervision of laboratory personnel during business hours and is locked with restricted key access during all other hours.

Motor cortex stimulation for upper limb: The TMScoil is placed with its center near the vertex in the optimal position and orientation for producing a motor evoked potential (MEP) in the bicep, tricep, abductor pollicis brevis (APB) muscle, first digital interosseous (FDI) muscle, or abductor digiti minimi (ADM) muscle, as the clinical context requires.

Motor cortex stimulation for lower limb: The motor cortex that controls leg and foot lies along the inter-hemispheric frontal lobe and can be better stimulated using the double cone coil over the vertex.

Cerebellar stimulation The cerebellum will be stimulated 1-2 cm lateral and caudal (below) the inion (the protuberance at the back of the head) as described by Ugawa and colleagues.¹²

Plexus stimulation The spinal cord will be stimulated with the patient prone and the figure 8 or round coil placed at the level of the cervical/brachial plexus or lumbar spine/plexus.

Priming cortex for children with high thresholds Some young children and all infants have high thresholds for stimulation. The low intensity, intermittent Theta Burst Stimulation (iTBS) potentiation protocol used in IRB approved protocols CHMC 2008-1237 and 2008-1256 will be used as needed to facilitate single and paired pulse TMS measures.

Repetitive Stimulation Repetitive stimulation of the cortex will be performed using Theta Burst Stimulation (TBS). TBS protocols are currently used in IRB approved protocol CHMC 2008-1256. The use of these protocols is well documented in the medical literature²⁸⁻³¹. For the CHMC 2008-1256 study, we have already performed TBS on 63 pediatric/adult subjects and all the subjects have tolerated the protocols well without serious adverse events.

Functional TMS Single and paired pulse TMS, as above, performed dominant or non-dominant motor cortex during bimanual tasks, response inhibition tasks, and reward paradigms. Functional TMS will also target cortical regions that are important for motor control and motor response inhibition. These regions will include supplementary motor complex and inferior frontal gyrus.

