Probabilistic Learning Probabilistic classification learning is a task that requires activation of the frontostriatal network, which modulates motor preparation and movements. The task performance has been shown to be abnormal in several movement disorders – Parkinson’s disease, Tourette Syndrome, Huntington Disease ³⁴⁻³⁶. This task involves the subject to predict a binary outcome (positive or negative) based on looking at a sequence of four items (i.e. cards).

Bimanual Tasks In each experiment, the child has both hands relaxed on his lap, on a pillow supporting at the elbows. For the single finger tapping motor task, the child is instructed to repeatedly tap the task hand index finger while keeping the non-task hand in the same position, but relaxed. To ensure consistency in performance speed and coordination, the a computer instructions will be shown to indicate resting, tapping one finger, tapping all fingers sequentially, and sustaining a squeezing of the index finger to the thumb. TMS will be administered as above but during the task.

Response Inhibition Tasks In each experiment, the child keeps both hands relaxed, but on a cue from the computer has to push an X button with the right hand or O button with the left hand, on a game controller. On some trials, a “stop” auditory tone will occur. At time = 0ms, an image of either an X or O will be displayed on the screen. TMS will be administered as above but during the task. Slater-Hammel procedure, another response-inhibition task, may also be used to assess motor response time ³⁷. This task requires the subject to hold a button and release before a moving marker reaches a predefined time point (800 milliseconds after the start signal). If the marker stops in its trajectory, the participant is instructed to not let go of the button. Another method of comparing response inhibition is to present conditions of just staring at computer screen vs. instructing subjects to activate or inhibit motor movement.

Reward Paradigm In each experiment, the participant watches while smiling or frowning faces appear on the computer screen. Three smiles will result in the participant receiving a monetary award (\$0.25). TMS will be administered as above, but during the task.

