VIII. POTENTIAL BENEFITS

There is a potential for direct benefit by participating in this study if the clinical neurophysiological information is useful to the managing physician.

IX. POTENTIAL RISKS, DISCOMFORTS, INCONVENIENCES, AND PRECAUTIONS

1. Known and potential discomforts or hazards of single and paired pulse TMS:
Single and paired pulse TMS has been used at CCHMC under [name] direction since 2001 for research only. Potential discomforts are mild and transient. In a prior study of 40 healthy and ADHD children, Garvey et al asked children to rank TMS compared to other childhood activities. TMS was ranked preferable to 1) a "shot"; 2) going to the dentist; and 3) a long car ride ⁴³. The following mild, transient effects were reported in our prior study of 35 children and adults: scalp discomfort (12%), hand weakness (9%), headache, neck pain, arm pain, and arm tingling (6%), hand pain, decreased hand dexterity, hearing changes, and tiredness (3%). All of these had resolved by the following day. There were no physical findings after TMS supporting the subjective descriptions of loss of strength or dexterity. Furthermore, a consensus statement from the international TMS community concluded that "single-pulse and paired-pulse TMS in pediatrics is safe for children two years and older."⁴⁴ A prior common concern about use of TMS was the risk of seizures⁴⁵. We follow recommended guidelines ⁴⁵ and have seen no seizures in children or adults studied at our center. In addition, more recent studies even in children with epilepsy suggest that the risk of TMS inducing seizures is quite low.

2. Precautions, risk minimization:

The protocols include a number of precautions to minimize risk. The TMS laboratory was established in 2001 in consultation with [name], an internationally known researcher in transcranial magnetic stimulation. [name] or [name] will be present during TMS. All subjects will wear 34 NRR earplugs or headphones during TMS if the head is stimulated at an intensity of over 90%. Standard exclusion criteria are applied for participation in this study. Detailed questioning for any adverse events will occur after the experiment and the next day after the study.

3. The method of monitoring study conduct.

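### Does requiring ear protection only above 90% intensity confound the auditory stop task with motor threshold and age?

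*Combined protocol and SAP*

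**What the plan says.** The only ear rule for TMS is in section IX.2 (Precautions, risk minimization): "All subjects will wear 34 NRR earplugs or headphones during TMS if the head is stimulated at an intensity of over 90" per cent. The unit is not stated, and nothing is said about stimulation at or below that level. The other earplug instruction, under Brain MRI in section VI.4, concerns the scanner only.

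Under Response Inhibition Tasks in section VI.4, the stop signal in the X/O game is a sound: "auditory tone will occur. At time = 0ms, an image of either an X or O will be displayed on the screen". The paragraph continues: "TMS will be administered as above but during the task". It gives no tone level, delivery route or ear condition.

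On intensity, the Functional TMS paragraph says: "Single and paired pulse TMS, as above, performed dominant or non-dominant motor cortex during bimanual tasks, response inhibition tasks, and reward paradigms". It adds further targets ("These regions will include supplementary motor complex and inferior frontal gyrus") without stating an intensity for them. Under Neurophysiological parameters the protocol says "Thresholds defined using conventional criteria as the lowest stimulator intensity that produces measurable responses in 3 of 6 trials" and "Subthreshold pulse precedes suprathreshold pulse for paired pulses". No multiple of threshold is given. For children with high thresholds, low-intensity theta burst priming "will be used as needed to facilitate single and paired pulse TMS measures".

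Section V gives threshold data from another study of ADHD and typical children aged 8 to 12: mean 68% of maximal stimulator output, SD 16%, and a correlation with age of -.63 in 72 children.

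**The concern.** The cue that defines a stop trial is a sound, and the protocol makes ear protection depend on stimulation intensity. Section V reports thresholds as a percentage of stimulator output, and they fall with age. If the 90% is on that same scale and task pulses are set relative to each person's threshold, younger or high-threshold participants would more often hear the tone through earplugs or headphones than older ones.

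A later comparison of stopping by age, by threshold, or between groups that differ in either could then partly reflect ear condition. Section VI.4 lists effect and sample size calculations for future studies among the uses of the data, so a distorted between-person difference could carry into a later design. If ear condition were not recorded, it could not be separated from age afterwards.

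**Working it through.** **Inputs.** From section V: threshold mean 68, SD 16 (% of maximal stimulator output), r = -.63 with age, n = 72. From section IX.2: the cut-off of 90. Assumed: 90 is on the stimulator-output scale, task pulses are k times threshold (k is not in the documents), and threshold and age are jointly normal.

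**The protocol's own figure.** Section V reports p < .001 for the correlation. t = r√[(n-2)/(1-r²)] = -.63 × √(70/0.6031) = -6.79 on 70 df, so p is about 3 × 10⁻⁹. The stated figure is consistent. The Fisher-z 95% interval for r is -.752 to -.466.

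**Threshold by age.** At one SD below and above mean age, the mean threshold is 68 ± 0.63 × 16 = 78.08 and 57.92. The residual SD is 16 × √(1 - 0.63²) = 12.43.

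**Share required to wear protection.** Protection is required if kT > 90, and a child is testable if kT ≤ 100. Among testable children the share is [P(kT > 90) - P(kT > 100)] / [1 - P(kT > 100)].

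Worked for k = 1.2, where the cut-offs on T are 90/1.2 = 75 and 100/1.2 = 83.33:
- Younger: P(T > 75) = 59.8% and P(T > 83.33) = 33.6%, so (59.8 - 33.6)/(100 - 33.6) = 39.4%.
- Older: P(T > 75) = 8.5% and P(T > 83.33) = 2.0%, which gives 6.6% from unrounded values.

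| Assumed k | Younger, testable | Older, testable | Younger needing over 100% output |
|---|---|---|---|
| 1.0 | 13.5% | 0.5% | 3.9% |
| 1.1 | 27.2% | 2.3% | 15.1% |
| 1.2 | 39.4% | 6.6% | 33.6% |
| 1.3 | 48.6% | 12.6% | 53.7% |

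The last row describes fewer than half of the younger group, because the rest could not be tested at that intensity.

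**Sensitivity at k = 1.2.** Over the interval for r, the contrast runs from 49.2% vs 3.1% to 31.5% vs 10.5%. If 90% means 90% of individual threshold, every suprathreshold pulse requires protection: 100% vs 100%, with no gradient.

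**From these shares to a biased result.** Each of the following would have to hold:
1. The 90% is stimulator output. This is plausible, because section V gives the only percentage scale for intensity, but it is not stated. Elsewhere stimulation is described in Tesla.
2. Task pulses scale with individual threshold. This is only suggested, by the sub- and suprathreshold wording for paired pulses.
3. Staff protect only those above the cut-off. The rule is a minimum and does not say this.
4. Protection changes how the tone is heard enough to alter stopping or evoked potentials. The documents have no data on this.
5. Someone compares people who differ in threshold or age. No such comparison is specified.

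The arithmetic covers only what follows from links 1 and 2. The size of any bias cannot be computed from the documents.

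**The case for a change.** The strongest case for acting is that the gap is real and cheap to close. The registered title is about response inhibition in Tourette syndrome, so the task family is not peripheral. The cut-off falls inside the range of likely pulse intensities, so under the output reading it would split the sample by age and not cover all or none. Enrolment runs from over 2 to under 60 years, and the protocol itself says some young children have high thresholds. Section VI.8.b looks ahead to disease-versus-control differences in future studies. Even under the other reading of 90%, earplugs and headphones remain interchangeable and the tone level is unset.

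The textual points and the arithmetic stand. The step to a wrong result does not. The threshold figures come from a different study with a narrower age range and no Tourette data, and the coil and stimulator behind them are not stated. Section VI.4 also refers to four other IRB protocols for the TMS set-up, where task intensities or ear practice may be described. An omission here therefore does not show that the condition is uncontrolled in the laboratory.

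What remains is a request for operating detail. Noting ear condition and stimulator intensity for each tone-task session would be sensible record-keeping, and staff can do it without an amendment.

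**Conclusion.** The concern does not call for a change. The protocol does leave the unit of 90% unstated, and it fixes no ear condition or tone delivery for the auditory stop task. Under two unconfirmed assumptions, required protection would differ by age: about 39% against 7% at an assumed 120% of threshold, within the output ceiling and on borrowed threshold data. That is a difference in who wears earplugs or headphones, and nothing in the documents turns it into a bias in stopping or in evoked potentials.

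The setting limits the consequence further. Behavioral tasks are optional, section VI.8 plans no statistical analyses, and section VI.8.b says this is not a formal case-control study. Stop-versus-go contrasts within a participant under one ear condition are unaffected, and the Slater-Hammel stop cue is visual. Following the protocol as written gives no demonstrably wrong result. The gap is one that the laboratory and any later analyst can fill sensibly. The conclusion would need another look if a between-person comparison of stop-tone performance were made a formal analysis.
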